### **Secondary Objectives**

1. Quantify the amount of tumor necrosis before and after initial treatment in both groups by CT volumetry, and correlate with response to treatment by RECIST criteria.
2. Evaluate toxicity, time to progression (TTP) and survival in each treatment arm.  
Determine if initial imaging response to treatment, as manifested by either RECIST criteria or volume of necrosis correlates with either TTP (by RECIST or volumetric method) or survival.

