The expected outcomes of this study are to determine the response to treatment following arterial embolization of HCC using microspheres alone or microspheres + doxorubicin by RECIST criteria, and to determine the % tumor necrosis that results following treatment in each group. The response to treatment by RECIST criteria will be correlated with % tumor necrosis in both groups, and the relationship of both of these response parameters to TTP and survival will be assessed. The study may serve to validate an automated volumetric method of assessing response to treatment, and determine if this imaging response to treatment can be used as a surrogate biomarker for outcome. The findings will increase our understanding of how regional hepatic arterial therapies work, and may improve upon current imaging methods of assessing response to treatment. This study will offer a preliminary assessment of whether the additional expense, complexity, and potential side effects of adding chemotherapy to arterial embolization are worthy of further investigation. The results of this study are important not only for patients with HCC, but also for patients with other hypervascular liver tumors that are commonly treated with hepatic embolization.

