#### Tumor Response

For the purposes of the primary objective, the triple phase CT obtained within 2-3 weeks of initial treatment will be used to assess response to treatment. Tumor response will be catalogued according to RECIST criteria as well as by % necrosis determined using the study CT volumetric method.

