### **Time to Progression**

Time to progression (TTP) will include and be categorized as time to: local tumor progression (LTP), distant hepatic progression (DHP), and extra-hepatic progression (EHP). Local tumor progression (LTP) will be measured as the time from randomization until the first measurement of progression as determined by the central reading group using RECIST criteria as well as volumetric criteria for the target tumor. Local tumor progression (LTP) will be defined specifically as  $\geq 20\%$  increase from the smallest sum of measurements since the start of treatment (RECIST criteria, see above), or  $\geq 75\%$  increase in enhancing tumor volume. Distant hepatic progression (DHP) will be defined as the development of any new discontinuous disease within the liver, and the development of any extra-hepatic disease will constitute extra-hepatic progression (EHP).

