## 10.0 EVALUATION DURING TREATMENT/INTERVENTION

Time line	Within 6 weeks	Within 4 weeks	Within 2 weeks 	Time 0	Day 1	10-14 Days	Within 2-3 weeks	10-14 weeks	5-6 months	8-9 months	11-12 months
Clinic Visit 	X		X				X 	X	X	X	X
Laboratory tests											
CBC		X	X		X	X 	X	X	X	X	X
PT, INR, PTT		X	X				X	X	X	X	X
electrolytes		X	X				X	X	X	X	X
BUN/creatinine		X	X				X	X	X	X	X
AFP		X	X				X	X	X	X	X
Albumin, total protein, bilirubin (total)			X	X			X	X	X	X	X
LDH, Alk. Phosphatase, ALT, AST			X	X			X	X	X	X	X
Hepatitis screening (B and C)			X 								
Radio logic tests											
Triple phase CT (TPCT)	X						X 	X 	X 	X 	X 
Treatment											
Hepatic Embolization procedure				X 							
Others											
ECG		X									
MUGA scan or Cardiac Echo			X 								
ECOG assessment								X	X	X	X
Vital Signs checked	X		X				X	X	X	X	X

For patients randomized to the LC Bead (particle + doxorubicin) group. Patients will have repeat MUGA scan or cardiac echo after every 3 treatments, or 450 mg of doxorubicin, and prior to exiting protocol if feasible. If patient exits protocol unexpectedly (e.g. due to death), no MUGA scan or cardiac echo is necessary.

Only for patients who require 2 embolizations to complete one treatment, within 2 weeks of the second embolization the patient will return for clinic, vitals and laboratory tests.

Time 0 is the day of the patient's completed treatment, either single or two embolizations sessions, as anticipated by pre-treatment CT.

CBC may be done locally.

CT used to determine response to treatment.

CT used to determine the need for re-treatment.

If there is evidence of disease progression; a repeat treatment will be scheduled within 2 months  $\pm$  2 weeks. The patients will be re-treated with the same embolic agent used in the first treatment. Patients will not receive more than 450 mg of doxorubicin per annum. They will then re-enter the follow-up pathway.

 Clinic visit will include recording of vital signs, ECOG status and assessment of any SAE

 No ECOG assessment will be done at 2-3 weeks post embolization visit since patients might still be experiencing post-embolization syndrome

If not already done.

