## **Time 0 + 2-3 weeks**

Patients will be seen in clinic within 2-3 weeks of complete treatment (Time 0). They will have vital signs (weight, blood pressure, temperature, and heart rate), CBC, chemistry profile with liver function tests, coagulation studies, AFP level, and evaluation of any treatment toxicity. The patients will also have a triple phase CT scan. This is the CT scan that will be used to determine response to treatment

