Another secondary objective is to establish whether the use of the doxorubicin eluting beads might prolong time to progression (TTP), or survival, and if initial imaging response to treatment, as manifested by necrosis, correlates with either endpoint. This aim relates to analysis with censored outcomes (time-to-progression and survival time). We will use the Kaplan-Meier method to estimate the survival probabilities and we will use the log-rank test to compare groups. With 50 patients in each arm, we will have approximately 80% power to detect a hazard ratio of 3, assuming a median follow-up of 3 years (i.e., about half of the patients expiring) and controlling the Type I error rate at 5%. A hazard ratio of 3 corresponds to improving the median survival by three-fold or improving two-year survival by approximately 20%. We do not anticipate a survival difference of this magnitude so this aim will primarily serve to obtain preliminary data to plan a future definitive trial.

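### RECIST response is to be related to TTP counted from randomization, so progression on the response CT is both a non-response and a TTP event; a landmark at that CT removes the overlap

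*Combined protocol and SAP*

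**What the plan says.** Section 2.0 (Secondary Objectives) asks whether initial imaging response, "as manifested by either RECIST criteria or volume of necrosis correlates with either TTP (by RECIST or volumetric method) or survival". Section 14.0 restates the aim for necrosis only: "if initial imaging response to treatment, as manifested by necrosis, correlates with either endpoint".

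The predictor is read after treatment. Section 4.1 (Tumor Response) says "the triple phase CT obtained within 2-3 weeks of initial treatment will be used to assess response to treatment", and Section 10.0 says of the visit 2-3 weeks after Time 0: "This is the CT scan that will be used to determine response to treatment". A footnote to the Section 10.0 schedule adds: "Time 0 is the day of the patient's completed treatment, either single or two embolizations sessions".

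The outcome starts earlier. Section 4.1 (Time to Progression) says: "Local tumor progression (LTP) will be measured as the time from randomization until the first measurement of progression". No time origin is given for survival.

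The RECIST tables in Sections 4.1 and 12.0 define PD as a rise of at least 20% in the sum of measurements. Section 4.1 uses the same rise as the local progression event. Section 12.0 repeats the linear and volumetric readings at every scan and exempts none.

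The methods named in Section 14.0 for censored outcomes are Kaplan-Meier and the log-rank test. It mentions no landmark, no time-dependent covariate and no exclusion of patients who have already progressed. Section 3.0 gives a wider purpose, which is to "determine if this imaging response to treatment can be used as a surrogate biomarker for outcome".

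**The concern.** On the response CT the only earlier measurement is baseline, so a 20% rise counts as PD for response and as progression for TTP. A patient with that rise enters the non-responder group and has a TTP event from the same scan. A RECIST responder cannot have target-lesion progression on it. Responders are thus protected by definition from the earliest local progression events, whether or not response says anything about what happens later.

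The stake is how the association is read. Section 14.0 wants this aim to supply preliminary data for a definitive trial, and Section 3.0 hopes to learn whether imaging response can stand in for outcome. An association that comes partly from the definitions could mislead both uses.

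**Working it through.** The plan gives no figure for the response-outcome analysis. Its power statement in Section 14.0 concerns the comparison of arms and is not used here.

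**Inputs from the documents.** There are 100 patients. The response CT is 2-3 weeks after completed first treatment. A second session, where needed, follows 2-6 weeks after the first, so the CT then falls 2+2 = 4 to 6+3 = 9 weeks after the first embolization. **Assumed, because the documents give no values:** the share of responders, the share with PD on the response CT, and the rate of later progression.

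**Hand check of the mechanism (30 responders, 10 PD, 100 patients).** At the response CT there are 10 events, none in responders. The log-rank test expects 10 × 30/100 = 3 in responders, so observed minus expected is -3. The variance at that time is 10 × 0.3 × 0.7 × 90/99 = 1.91. If all 90 others later progress at separate times, independently of response, they add mean 0 and variance of about 90 × (1/3) × (2/3) = 20. The test statistic is then centred at -3/√21.91 = -0.64 with SD √(20/21.91) = 0.955. The chance of exceeding 1.96 in absolute value is Φ(-1.32/0.955) + Φ(-2.60/0.955), about 0.084 + 0.003, or 9% rather than 5%. Tied scan dates and incomplete follow-up leave less dilution, so simulated values run higher.

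With 10 responders and 10 PD, observed minus expected is only -1. The variance is 10 × 0.1 × 0.9 × 90/99 + 90 × (1/9) × (8/9) = 0.82 + 8.89 = 9.71, and the centre is -1/√9.71 = -0.32. The same calculation gives about 5%.

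**Simulation under no true later association.** Later progression is exponential and identical in all patients, with a mean of 12 months. Scans follow every 3-6 months, and PD patients have their event at the response CT. Responders are compared with non-responders by log-rank.

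| Responders | PD on response CT | False-positive rate from randomization | Range over repeat runs |
|---|---|---|---|
| 30% | 10% | 10% | 9-11% |
| 30% | 15% | 18% | 16-18% |
| 50% | 10% | 24% | 22-26% |
| 50% | 15% | 42% | 41-46% |

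A second set-up (1,500 runs) puts the CT 1.5 months after randomization, with a median residual TTP of 8 months and follow-up to about a year:

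| Responders | PD on response CT | False-positive rate | Apparent hazard ratio, non-responder vs responder |
|---|---|---|---|
| 10% | 5% | 4.4% | 1.08 |
| 10% | 10% | 4.9% | 1.19 |
| 10% | 20% | 8.4% | 1.38 |
| 30% | 0% | 5.1% | 0.99 |
| 30% | 5% | 5.7% | 1.12 |
| 30% | 10% | 13.3% | 1.23 |
| 30% | 20% | 38.2% | 1.51 |

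**With a landmark at the response CT**, leaving out patients already progressed, the false-positive rate is about 4-7% across both set-ups. In the second set-up the apparent hazard ratio is 0.98-1.01.

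**Necrosis.** Under the volumetric method in Section 12.0, tumor voxels below a threshold are necrosis. I take enhancing volume as the rest, V(1 - f), with f the necrotic fraction. Volumetric progression is a rise of about 75% in that quantity. If f = 0 at baseline (an assumption), a scan with f = 5% meets it when total volume reaches 1.75/0.95 = 1.84 times baseline. With f = 50%, the threshold in Section 14.0, total volume must reach 1.75/0.50 = 3.5 times. Predictor and volumetric event therefore share a measurement. No false-positive rate was derived for this. If RECIST PD is independent of necrosis group (half of patients in the high group, 10-15% PD), the rate is 5.5-5.7%, so there is no inflation by that route.

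**Survival.** A patient must be alive at the CT to be classified. Section 3.0 cites 85% one-year survival in the institution's own series, a hazard of -ln(0.85) = 0.1625 per year. Expected deaths per 100 are 100 × (1 - exp(-0.1625 × 3/52)) = 0.9 by week 3 and 4.0 by week 13. Week 13 is the 9 weeks above plus an assumed 4 weeks from randomization to first embolization. If those patients simply have no response value, a simulation gives a 4.5% false-positive rate.

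**The case against.** The strongest case on the other side has four parts.

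- **The analysis is not spelled out.** Section 14.0 says log-rank will compare groups and then speaks of the two arms. It does not expressly specify a responder versus non-responder log-rank from randomization. This stands in part: the exact test is a reconstruction. But the objective, the time origin and the methods are all stated, and nothing in the plan rules this analysis out.
- **The inflation may be absent.** The CT comes early, and Section 3.0 warns that RECIST was insensitive in other tumors that become necrotic, so there may be few responders. This stands: with few responders or little PD the effect is negligible. The documents give no expected shares, so the plan cannot rule out the harmful range.
- **The Section 14.0 sentence is about necrosis.** A reader might infer that PD and high necrosis exclude each other as PD and RECIST response do. The documents do not support that. Section 4.1 treats necrosis as continuous, and the Figure 2 caption in Section 12.0 describes a tumor whose volume rose 29.5% while its necrosis ratio rose 388.8%. The direct overlap rests on the RECIST half of the objective in Section 2.0.
- **The aim is exploratory.** Section 14.0 disclaims hypothesis testing, and the surrogate language in Section 3.0 is hedged. This limits the weight of the point but does not remove the bias from an estimated association.

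A reader might also infer that survival is affected in the same way. It is not: progression on a CT is not a death, and no time origin for survival is stated. Nor does the plan say that patients who die before the CT become non-responders.

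**Conclusion.** The point holds for RECIST response against TTP, through local (target-lesion) progression. Followed as written, the plan could produce an association with no predictive content. The false-positive rate is about 10-18% with 30% responders and 10-15% PD on the response CT, and about 24-42% with 50% responders. It is negligible with 10% responders and 10% PD, or with 30% and 5%. These figures rest on assumed response and PD shares and on exponential later progression.

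For necrosis the overlap is indirect, through enhancing volume, and its size was not quantified. For survival the only issue is being alive at the CT, and its effect is small. A reader might infer that the planned analysis is certain to show an association; the low-share scenarios contradict that. The point is worth acting on because the remedy is cheap, but it concerns a secondary aim and leaves the primary response-rate estimates untouched.

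**What to change.** In Section 14.0, state that the response-outcome analyses:

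- start from a landmark at the response CT and are adjusted for arm;
- for TTP, include patients alive and progression-free at that CT;
- for survival, include all patients alive at that CT, including those with PD, with time counted from the CT;
- for necrosis, use RECIST TTP as the main progression outcome, and still report volumetric TTP, as Section 2.0 plans, with a note that it shares its measurement with necrosis;
- are described as patient-level associations, not as surrogate validation.

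This changes analysis wording only and needs no new visits, scans or patients. The cost is that the TTP analysis loses patients who have progressed or died by the first CT, and their number should be reported by arm. The landmark does not cure one further limit. Section 13.0 takes patients with very low necrosis after initial treatment off study, so later progression data may be missing in relation to the predictor. The report should say so.

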### **Time to Treatment Failure**

Time to treatment failure (TTF) will be measured as the time from randomization until treatment discontinuation for any reason including, development of  $\leq 5\%$  necrosis, by volume, following the initial treatment or  $>50\%$  increase in sum of uni-dimensional measurements following later treatments, treatment toxicity, patient preference, or death.

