### **Time 0 + 11-12 months**

Patients will be seen in clinic and have vital signs (weight, blood pressure, temperature, heart rate), CBC, chemistry profile with liver function tests, coagulation studies, and AFP, and ECOG assessment. They will have a triple phase CT scan. Patients with stable disease compared to the previous scan will be followed up in 3 months. If there is evidence of recurrent or new tumor a repeat treatment will be scheduled within their original treatment arm within 6 weeks of the follow-up scan. The patients will be re-treated with same embolic agent used for first treatment, with embolization protocol identical to that outlined above. They will then re-enter the follow-up pathway. Within one year patients will not receive more than 3 embolizations with LC Bead in order to ensure that they are not exposed to >450 mg of doxorubicin/annum.

Patients who remain disease free (CR), or who have stable disease (SD) at this point, will have follow-up triple phase CT every 3-6 months until death or progression and will only be re-treated for progression or new tumor.

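### With Kaplan-Meier as the only estimator for time to progression, deaths without progression are by implication censored, so the proportions with local, distant hepatic and extra-hepatic progression would be overstated

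*Combined protocol and SAP*

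**What the plan says.** Section 14.0 introduces the time-to-event aim with "This aim relates to analysis with censored outcomes (time-to-progression and survival time" and then gives the method: "We will use the Kaplan-Meier method to estimate the survival probabilities and we will use the log-rank test to compare groups". It names no other estimator.

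The Time to Progression entry in Section 4.1 defines the endpoint: "Time to progression (TTP) will include and be categorized as time to: local tumor progression (LTP), distant hepatic progression (DHP), and extra-hepatic progression (EHP". For the local component, "Local tumor progression (LTP) will be measured as the time from randomization until the first measurement of progression". DHP is new discontinuous disease in the liver, and EHP is any disease outside it. Death is not an event in any of the three.

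The next endpoint but one in Section 4.1, time to treatment failure, does count death. Its list of reasons for stopping ends with "treatment toxicity, patient preference, or death".

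Section 14.0 expects substantial mortality, "assuming a median follow-up of 3 years (i.e., about half of the patients expiring) and controlling the Type I error rate at 5" percent. Under Time 0 + 11-12 months in Section 10.0, patients in complete response or with stable disease "will have follow-up triple phase CT every 3-6 months until death or progression".

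The protocol does not mention competing risks, cumulative incidence or progression-free survival. It does not state what happens in the TTP analysis to a patient who dies without progression.

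**The concern.** Kaplan-Meier treats a censored patient as someone who could still have the event later. A patient who has died cannot. If deaths are censored, one minus Kaplan-Meier estimates how many would progress if nobody could die first, and that exceeds the proportion who will actually progress.

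The components are more exposed than overall TTP. A patient who progresses locally and dies without spread outside the liver is a competing death for EHP, although not for overall TTP. More of the total mortality therefore competes with each component.

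Section 14.0 says that this aim serves mainly to supply preliminary data for a later definitive trial, and Section 3.0 says that an increase in TTP could help support a phase III study. Planning such a trial needs the proportion of patients expected to progress, by type. If deaths without progression also differed between arms, the two arms' curves would be inflated by different amounts.

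**Working it through.** **The plan's own figure.** The only number stated for this analysis is power: "With 50 patients in each arm, we will have approximately 80% power to detect a hazard ratio of 3". Half of 100 patients gives D = 50 events. By Schoenfeld, power = Φ(ln(HR)·√D/2 − 1.96) = Φ(1.0986 × 7.071/2 − 1.96) = Φ(1.92) = 97.3%. By Freedman, power = Φ(√D·(HR−1)/(HR+1) − 1.96) = Φ(1.58) = 94.2%. The stated 80% is not reproduced at 50 events; with 25 events Schoenfeld gives 78.4%. That is a separate matter, and nothing below depends on it.

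**Inputs from the documents**
- About half of the patients dead with 3 years of median follow-up (Section 14.0). Read as 50% survival at 3 years with a constant hazard, this gives an overall death hazard of ln 2/3 = 0.231 per year.
- Historical survival at the centre of 85%, 68% and 42% at 1, 2 and 3 years (Section 3.0, Preliminary Data). The 1-year figure gives −ln(0.85) = 0.163 per year; the 3-year figure gives −ln(0.42)/3 = 0.289 per year on average.

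**Inputs assumed, because the documents give none**
- Net 2-year progression of a given type, p, of 20%, 40%, 60% or 80%. The hazard is hp = −ln(1−p)/2, that is 0.112, 0.255, 0.458 or 0.805 per year.
- Hazard of death without that progression, hd, equal to a quarter, a half or all of 0.231, that is 0.058, 0.116 or 0.231 per year.

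**Formulas (constant hazards)**
- One minus Kaplan-Meier, deaths censored: 1 − exp(−hp·t)
- Cumulative incidence, death competing: hp/(hp+hd) × [1 − exp(−(hp+hd)·t)]

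**Worked case:** p = 40%, half of the death hazard.
- 2 years: 40.0% against (0.255/0.371) × [1 − exp(−0.742)] = 36.1%, an excess of 3.9 points.
- 3 years: 53.5% against (0.255/0.371) × [1 − exp(−1.113)] = 46.2%, an excess of 7.3 points.

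**Excess of one minus Kaplan-Meier, in percentage points, over p = 20-80%**

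| Share of death hazard acting first | 2 years | 3 years |
|---|---|---|
| Quarter (0.058) | 1.1 to 3.3 | 2.2 to 4.8 |
| Half (0.116) | 2.1 to 6.4 | 4.2 to 9.1 |
| All (0.231) | 3.8 to 12.1 | 7.5 to 16.8 |

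**If one progression type ended observation for the others.** Take net 2-year values of 30% LTP, 30% DHP and 10% EHP, with half of the death hazard. For LTP, one minus Kaplan-Meier is 30.0%. Cumulative incidence is 27.0% with death alone competing and 22.1% with the other two types competing as well. The plan does not say which situation applies.

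**The case against.** **The plan does not state this method.** A reader might infer that the protocol prescribes a Kaplan-Meier curve for each of LTP, DHP and EHP and orders deaths to be censored. It does neither. Section 14.0 refers to TTP as a whole, the three types come from Section 4.1, and the handling of death is not written down. That stands, and is why the point is put as an implication. It is still more than a missing detail: with progression as the only event and Kaplan-Meier as the only estimator, there is nowhere else for a death to go. Reading the method sentence as covering overall survival alone would leave TTP without an estimator, although the sentence before it names TTP.

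**Censoring at death targets a legitimate quantity, and Kaplan-Meier for overall TTP is conventional.** Both statements are true. But the net curve describes patients only if those who died would otherwise have progressed at the same rate as those still followed, which the data cannot show. It also does not give the proportion expected to progress, which a later trial needs. Convention is a reason to keep the Kaplan-Meier curve for overall TTP, not to make it the only estimate.

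**Death is captured elsewhere.** Overall survival is analysed, and time to treatment failure includes death. A difference in mortality would therefore be seen, but neither endpoint corrects the estimates by progression type.

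**The effect may be small.** A reader might take the expectation that half the patients will die as the rate of competing death. It is all-cause mortality and includes deaths after progression. With CT about every 3 months in the first year, many deaths may follow a recorded progression, and at a quarter of the death hazard the excess is only 1.1 to 3.3 points at 2 years. For comparison, Section 14.0 puts the precision of a proportion with 50 patients per arm at 14 points either way. This stands as a limit on importance. However, the confidence interval does not reflect this bias, and more patients would not reduce it.

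**Conclusion.** The point holds for the progression estimates, chiefly those by type. Following the plan as written, one minus Kaplan-Meier exceeds the proportion who will have a given type of progression whenever some patients die without it. Under constant hazards, net 2-year progression of 20-80%, and a quarter to all of a 0.231 per year death hazard acting first, the excess is about 1-12 points at 2 years and 2-17 points at 3 years. The documents do not show where in that range the trial would fall.

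Three stronger readings are not supported:
- A reader might use the 85% one-year survival (0.163 per year) to cap the competing death hazard. The same sentence's 42% at 3 years implies 0.289 on average, and Section 14.0 implies 0.231, so it is no cap. For the same reason, the 17 points is the top of an assumed range, not a bound.
- A reader might conclude that the arm comparison is invalid. With deaths censored, the log-rank test remains a valid comparison of cause-specific progression hazards. Overall survival and the primary response rate are untouched.
- A reader might expect the bias to favour one arm. The documents give no rate of death before progression in either arm, so unequal inflation is possible but not shown.

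The consequence is confined to a descriptive secondary aim. It is worth correcting because the direction of the error is known and the correction is cheap.

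**What to change.** In Section 14.0:
- State that death without progression is a competing event in the TTP analyses.
- Report cumulative incidence (Aalen-Johansen) by arm for LTP, DHP and EHP.
- For overall TTP, report cumulative incidence alongside the conventional Kaplan-Meier curve, and label what each one estimates.
- State whether one progression type ends observation for the others. If it does, treat the other types as competing events too.
- Keep the log-rank test, described as a cause-specific comparison, and keep Kaplan-Meier for overall survival.

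The cost is a few sentences of analysis wording. No additional patients, visits or scans are needed, and the methods are in standard software. The downside is that cumulative incidence is less directly comparable with published Kaplan-Meier TTP; keeping both curves for overall TTP limits that loss.
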